4.2 ALTERNATIVE DEFINITIONS OF THE PRIMARY EFFICACY ENDPOINT

4.2.1 Hb Response Regardless Use of Rescue Medication (for Sensitivity Analysis)

An alternative definition of the Hb response, for sensitivity analysis purposes, is defined as:

- Hb ≥ 11.0 g/dL and a Hb increase from baseline by ≥ 1.0 g/dL in subjects whose baseline Hb > 8.0 g/dL, or
- Increase in Hb ≥ 2.0 g/dL in subjects whose baseline Hb ≤ 8.0 g/dL.

at two consecutive visits with at least 5 days apart within the first 24 weeks of treatment regardless use of rescue therapy. Subjects who discontinue study medication before Hb response, as defined above, will be considered as non-responder.

4.3 SECONDARY EFFICACY ENDPOINTS

The secondary efficacy endpoints are for both US and Ex-US submissions unless specified otherwise:

US (FDA submission): The proportion of subjects who achieve a Hb response at two consecutive visits with at least 5 days apart during the first 24 weeks of treatment, without rescue therapy within 6 weeks prior to the Hb response. This analysis will be based on the ITT Population.

A Hb response is defined, using central laboratory values, as

- Hb ≥ 11.0 g/dL and a Hb increase from baseline by ≥ 1.0 g/dL in subjects whose baseline Hb > 8.0 g/dL, or
- Increase in Hb ≥ 2.0 g/dL in subjects whose baseline Hb ≤ 8.0 g/dL

Ex-US submission: Mean Hb change from baseline to the average level during the Evaluation Period, defined as Week 28 until Week 36 without rescue therapy within 6 weeks prior to and during the evaluation period. This analysis will be based on the PPS population.

- The time to achieve the first hemoglobin (Hb) response defined by the primary endpoint for Ex-US or the first secondary efficacy endpoint for the US submission.
- Proportion of patient exposure time (months) with Hb ≥ 10 g/dL during Weeks 28-52, similarly analysis for the period between Weeks 28 - 36
- Mean change from baseline in Low-density lipoprotein (LDL) cholesterol averaged over Weeks 12-24
- Mean change from baseline in Hb levels between Weeks 18 to 24 in patients whose baseline hs-CRP $>$ ULN
- Average monthly IV iron use per subject during weeks 28-52
- Time to first RBC transfusion during the treatment
- Mean change in mean arterial pressure (MAP) averaged over Weeks 8-12

- Time to first exacerbation of hypertension (defined as [systolic BP ≥ 170 mmHg AND systolic BP increase from BL ≥ 20 mmHg] or [diastolic BP ≥ 110 mmHg AND diastolic BP increase from BL ≥ 15 mmHg]) during weeks 28 to 52

4.4 ADDITIONAL EVALUATION OF EFFICACY

The additional efficacy evaluations in this study are:

- **Hb Correction and Maintenance:**
 - Hemoglobin maintenance: Mean change from baseline in Hb averaged over 8 weeks of treatment at Weeks 28 to 36, without rescue therapy within 6 weeks prior to and during this 8-week evaluation period.
 - Hemoglobin long-term Maintenance: Mean change in Hb averaged over 8 weeks of treatment at Weeks 44-52 without rescue therapy within 6 weeks prior to and during this 8-week evaluation period.
 - Mean change from baseline in Hb averaged over the 96 to 104 weeks of treatment, without rescue therapy within 6 weeks prior to and during this 8-week evaluation period.
 - Change from baseline in Hb at each of the selected post-dosing time points.
 - Proportion of subjects with Hb ≥ 10 g/dL averaged over Weeks 28-36, without rescue therapy within 6 weeks prior to and during this 8-week evaluation period.
 - Proportion of subjects with mean Hb < 9 g/dL, 9- <10 , 10- <11 , 11- <12 , 12- <13 , ≥ 13 g/dL during Weeks 28-36
 - Proportion of patient exposure (PEY) with Hb < 9 g/dL, 9- <10 , 10- <11 , 11- <12 , 12- <13 , ≥ 13 g/dL during weeks 28 to 52
- **Hospitalizations:**
 - Time to first hospitalization (% of subjects) up to Week 52.
 - Time to first hospitalization or skilled nursing facility (% of subjects) up to Week 52
 - Number of days of hospitalizations per patient-exposure year (PEY).
 - Number of days of hospital or skilled nursing facility per PEY
 - Number of medical-facility free days (hospital, skilled nursing facility, emergency room, or overnight observation) per PEY
 - Number of days on treatment out of hospital and skilled nursing facility up to Week 52, 7 days after Last Dose.
- **Missed dialysis sessions up to Week 52**
 - Occurrence (number) of missed dialysis sessions
 - Proportion of subjects with missed dialysis sessions
 - Number of days of missed dialysis sessions per patient-exposure year (PEY)

- **Rescue Therapy Use up to Week 52:**
 - Proportion of subjects who receive RBC transfusions.
 - Number of RBC packs per patient-month exposure to study medication.
 - Roxadustat subjects: The proportion of subjects requiring ESA rescue therapy (ATC code: B03XA01)
- **Changes in Cholesterol Levels:**
 - Change at each of the protocol specified treatment time points in:
 - total cholesterol,
 - low-density lipoprotein (LDL)/high-density lipoprotein (HDL) ratio,
 - non-HDL cholesterol.
 - Proportion of subjects achieving LDL target of <100 mg/dL averaged over Weeks 12-24 of treatment.
- **Blood Pressure Effect:**
 - Time to an exacerbation of hypertension over weeks 28-52, meeting at least 1 of the following criteria: Increase in blood pressure: An increase from baseline of ≥ 20 mm Hg systolic BP and sBP >170 mmHg or an increase from baseline of ≥ 15 mm Hg diastolic BP and dBP >100 mmHg.
 - Proportion of subjects achieving blood pressure treatment goal in ESRD subjects (pre dialysis systolic BP <140 mmHg and diastolic BP <90 mmHg) averaged over Weeks 12-28.
- **Health Related Quality of Life (HRQoL) and EQ-5D-5L Benefits of Anemia Therapy:**

Mean change averaged over Weeks 12, 36 and 52 of treatment including those listed below.

 - Vitality Sub-score of SF-36:
 - In FAS subjects with baseline Vitality Sub-score below 50.
 - In all FAS subjects.
 - Physical Functioning Sub-scores of SF-36:
 - In FAS subjects with baseline *Physical Functioning Sub-scores* below 40.
 - In all FAS subjects.
 - Anemia Subscale (“Additional Concerns”) of Functional Assessment of Cancer Therapy-Anemia (FACT-An) Scores:
 - In FAS subjects with baseline subscale scores below 55 (generally associated with fatigue).
 - In all FAS subjects.

- Total FACT-An Scores:
 - In FAS subjects with baseline FACT-An scores below 135
 - In all FAS subjects.
- EQ-5D-5L Scores and other QoL Measures/Other Component scores of SF-36: In all FAS subjects.
- **Hepcidin, Iron, C_Hr and HbA1c:**
 - Change from baseline in serum hepcidin at each of the selected time points (e.g., Weeks 4, 12, 20, 44 and every 8 weeks onwards)
 - Change in serum iron from baseline to Week 28
 - Change in TSAT from baseline to Week 28
 - Change from baseline in serum ferritin at each of the selected time points, total and sub-grouped by baseline values of, ≥ 400 ng/mL, 400 to 100 ng/mL, and <100 ng/mL.
 - Change from baseline in TSAT at each of the selected time points, total and sub-grouped by baseline values of $\geq 40\%$, 40% to 20%, and $<20\%$.
 - Serum iron at each of the time points tested
 - Change from baseline in C_Hr at each of the selected time points (e.g., Weeks 4, 8, 12, 20, 28, 36 and every 8 weeks onwards)
 - Proportion of patients with C_Hr $>$ LLN at each timepoint tested: Weeks 4, 8, 12, 20, 28, 36, and every 8 weeks onwards)
 - Change from baseline in HbA1c level at each of the selected time points in subjects without history of diabetes, in subjects with history of diabetes, and all subjects.
 - Changes from BL to each study visit (when measured) in fasting blood glucose,

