9 STUDY MEDICATION

9.1 EXTENT OF EXPOSURE

Exposure to study medication will be summarized by treatment group in terms of treatment duration in weeks, which is calculated using the following formula: (the date of last medication taken - the date of first dose taken +1)/7.

Total weekly study drug exposure is defined as the total prescribed dose (in mg and mg/kg for Roxadustat and IU and IU/kg for EPO) of study drug administered within the week (windowed by 7-day period from Day 1).

Duration of exposure, weekly exposure and total study drug exposure will be tabulated by treatment group for the safety population.

Per administration amount and administration frequency will also be tabulated by treatment group for the safety population and PPS population.

Patient-Exposure-Year (PEY) is defined as (Last Dose Date – First Dose Date + 1)/365.25.

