11.3.3 Missed Dialysis Sessions

Missed dialysis sessions are collected in the Dialysis Modality Form of the eCRF. For each subject, an entry will be recorded for missing dialysis. The number of missing dialysis will be summarized by treatment group.

The following missing dialysis-related data will be analyzed and compared between the 2 treatment groups:

- Occurrence (number) of missed dialysis sessions. The number of missed dialysis sessions for each subject will be collected. The mean number of missed dialysis sessions will be analyzed and compared between the 2 treatment groups using Mantel-Haenszel mean score test adjusting for stratification factors.
- Proportion of subjects with missed dialysis sessions. The proportion of subjects missed dialysis sessions will be compared between the 2 treatment groups using CMH model and stratified by the baseline stratification factors.
- Number of days of missed dialysis sessions per patient-exposure year (PEY). The number of days of missed dialysis sessions for each subject will be calculated (# of missed dialysis/weekly prescribed dialysis frequency* 7), where weekly prescribed dialysis is TIW in this study. The mean number of days of missed dialysis sessions will be analyzed and compared between the 2 treatment groups using the Mantel-Haenszel mean score test adjusting for stratification factors.

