11.3.4 Rescue Therapy Use

11.3.4.1 Blood Transfusion

For a subject receiving RBC transfusion, the Time at Risk (time up to first RBC transfusion) will be calculated (in years) as:

$$(\text{First RBCtransfusion date} - \text{First dose date of study medication} + 1) / 365.25$$

For a subject not receiving transfusion, the Time at Risk (time until they get censored) is calculated as:

$$(\text{Date of last study medication} - \text{First dose date of study medication} + 1) / 365.25$$

The blood transfusion form of the eCRF in the cumulative visit will be used to derive the number of RBC packs. The number of RBC units is collected in this form. For transfusions where the number of units is not given but the volume transfused is given, the number of units will be estimated by dividing the volume transfused by 250 mL (for transfusion of packed cells) or by dividing the volume transfused by 500 mL (for transfusion of whole blood).

The total number of RBC units/packs during the treatment period is calculated for each subject by the sum of the transfused units between the Analysis Date of First Dose and up to the Analysis Date of Last Dose. The following 2 endpoints will be analyzed:

- Proportion of subjects who receive RBC transfusions. The proportion of subjects who received RBC transfusion will be compared between the 2 treatments using logistic regression model adjusting for baseline stratification factors.
- Number of RBC packs per patient-month exposure to study medication. The mean number of RBC packs will be compared between the 2 treatment groups using ANCOVA model with baseline hemoglobin as covariate and treatment and stratification factors as fixed effect.

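### Missed-dialysis days are limited to Week 52 but expressed per patient-exposure year, and the SAP defines that exposure only over the whole treatment period; the RBC-pack rate is given two different windows

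*SAP*

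**What the plan says.** **Missed dialysis.** The heading in SAP 4.4 is "Missed dialysis sessions up to Week 52". Three items stand under it: the number of missed sessions, the proportion of subjects with any, and days missed per PEY. SAP 11.3.3 repeats the last item ("Number of days of missed dialysis sessions per patient-exposure year (PEY") and gives the day count: "The number of days of missed dialysis sessions for each subject will be calculated (# of missed dialysis/weekly prescribed dialysis frequency* 7". It states no Week 52 limit. The comparison it then describes is on days: "The mean number of days of missed dialysis sessions will be analyzed and compared between the 2 treatment groups using the Mantel-Haenszel mean score test".

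**Exposure.** The SAP has one formula for PEY, in 9.1: "Patient-Exposure-Year (PEY) is defined as (Last Dose Date – First Dose Date + 1)/365.25". It carries no cap. SAP 3 allows treatment for up to about 3 years after the last subject is randomized, and 9.1.2 has an open top exposure category above 156 weeks.

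**RBC packs.** SAP 4.4 has the heading "Rescue Therapy Use up to Week 52", with "Number of RBC packs per patient-month exposure to study medication" beneath it. SAP 11.3.4.1 says "The total number of RBC units/packs during the treatment period is calculated for each subject", summing from first to last dose. Patient-month exposure is not defined anywhere.

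**Protocol.** Section 7.3 lists missed dialysis sessions and RBC packs per patient-month without a Week 52 limit. The window was added in the SAP.

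**The concern.** A rate is interpretable only if events and time at risk cover the same period. If missed sessions stop counting at Week 52 but exposure runs to last dose, each week on drug after Week 52 adds to the denominator and can add nothing to the numerator. Subjects treated for 52 weeks or less are unaffected; the others have their rates diluted, more so the longer they stay on drug.

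Two things follow. The reported rates no longer describe how often dialysis was missed. And if one arm stays on drug longer after Week 52, it shows a lower rate even when the true rates are equal. In an open-label trial unequal discontinuation is plausible, and SAP 6 plans Kaplan-Meier plots of premature discontinuation by arm.

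For RBC packs the stake is different. Two analysts following two sections of the same SAP would report rates over different periods, each with a denominator of their own choosing.

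**Working it through.** The documents state no figure for these rates, so there is nothing to reproduce first.

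**Step 1: the windows side by side**

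| Endpoint | Events in SAP 4.4 | Events in analysis section | Exposure |
|---|---|---|---|
| Missed-dialysis days per PEY | up to Week 52 | 11.3.3: no window stated | 9.1: first to last dose, uncapped |
| RBC packs per patient-month | up to Week 52 | 11.3.4.1: first to last dose | no formula |

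For missed dialysis, joining the 4.4 window to the defined term in 9.1 gives a mismatch. For RBC packs, the two event windows contradict each other and the denominator is open.

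**Step 2: effect on one subject**

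Inputs: the Week 52 limit (4.4), the PEY formula (9.1) and a constant true rate (assumed). With *w* weeks of exposure, *w* above 52:

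understatement = 1 − 52/*w*

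| Exposure (weeks) | 52/*w* | Understatement |
|---|---|---|
| 52 or less | (no time after Week 52) | 0% |
| 78 | 0.667 | 33% |
| 104 | 0.500 | 50% |
| 130 | 0.400 | 60% |
| 156 | 0.333 | 67% |
| 208 | 0.250 | 75% |

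Example: at a true rate of 6 days per PEY and 104 weeks on drug, days counted are 6 × 364/365.25 = 5.98, PEY is 728/365.25 = 1.993, and the reported rate is 5.98/1.993 = 3.0.

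**Step 3: effect between arms**

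The documents give no discontinuation rates, so all inputs in this step are assumed: equal true rate of 10 days per PEY, exponential time *T* to discontinuation, and administrative follow-up *C* uniform over a stated range. Writing 1 for the Week 52 cut (364/365.25 years in the calculation):

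pooled rate = 10 × E[min(*T*, *C*, 1)] / E[min(*T*, *C*)]

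| Follow-up (years) | Discontinuation per year | Pooled rate | False ratio |
|---|---|---|---|
| 0.7–3.5 | 0.25 | 10 × 0.870/1.585 = 5.49 | |
| 0.7–3.5 | 0.35 | 10 × 0.830/1.432 = 5.80 | 5.80/5.49 = 1.06 |
| 0.7–3.5 | 0.30 | 10 × 0.849/1.505 = 5.64 | |
| 0.7–3.5 | 0.45 | 10 × 0.793/1.300 = 6.10 | 6.10/5.64 = 1.08 |
| 1–4 | 0.30 | 10 × 0.861/1.705 = 5.05 | |
| 1–4 | 0.45 | 10 × 0.803/1.445 = 5.56 | 5.56/5.05 = 1.10 |

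The ratio is shorter-exposed over longer-exposed arm, and its true value is 1.00.

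A starker set of assumptions, with everyone followed to the same maximum and hazards of 0.25 against 0.40, gives 1.00 at 1 year, 1.06 at 2, 1.13 at 3 and 1.18 at 4. With equal hazards the ratio is 1.00 throughout.

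The SAP does not say whether rates are pooled or averaged over subjects. Averaged, a true rate of 10 becomes about 6.9 instead of 5.49 at hazard 0.25 and 0.7–3.5 years of follow-up; the arm ratios are similar.

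**Step 4: matched windows**

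If both parts stop at Week 52, or both run to last dose, the understatement is 0% at every exposure length and the ratio is 1.00 under equal true rates. For RBC packs, the 11.3.4.1 count over whole-treatment exposure is already matched.

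**The case against.** The best defence is that no sentence in the SAP divides a 52-week count by whole-treatment exposure. The result appears only when the 4.4 heading is joined to the general formula in 9.1. The heading covers the per-PEY item, so it can be read as limiting days and exposure alike, and 4.4 itself uses PEY inside a window, for haemoglobin bands over Weeks 28 to 52. Taken alone, 11.3.3 has no Week 52 limit, so whole-period days over whole-period PEY would match. Its described test is on mean days, so PEY may not enter the comparison at all.

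This stands in part. A careful analyst might well cap the exposure, and a reader who infers that the SAP expressly specifies the mismatched rate goes further than the text. But nothing instructs the cap, and 11.3.3 repeats the per-PEY endpoint without settling the window. The SAP also does elsewhere what is feared here: 11.2.1.4 is titled for Weeks 28 to 52, yet its written divisor for monthly IV iron runs from first drug date to last visit. Under Hospitalizations in 4.4, by contrast, the Week 52 limit sits on individual items and the per-PEY items carry none, so a heading-level limit has real effect.

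A reader might also infer that RBC-pack rates are understated in the same way. The documents do not support that: 11.3.4.1 counts packs to last dose, and patient-month exposure is undefined, so the PEY formula cannot be imported as its definition.

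**Conclusion.** The point holds, at minor severity. For missed dialysis, the Week 52 limit in 4.4 and the uncapped PEY in 9.1 do not fit together. Followed as written, they understate the rate of every subject treated beyond 52 weeks, by the amounts in step 2 if the true rate is constant. Two thirds is the value at 156 weeks and should not be taken as a ceiling, since the SAP foresees longer exposure.

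The between-arm effect is conditional. It needs different exposure after Week 52, and its size, about 1.06 to 1.10 in the main scenarios, rests on assumed discontinuation rates and follow-up. A reader might infer that the plan favours roxadustat; the documents do not show which arm, if either, will stay on drug longer.

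For RBC packs the finding is a contradiction between 4.4 and 11.3.4.1 plus an undefined denominator.

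All of these are additional efficacy endpoints. They are not in the fixed sequence of SAP Table 5, and SAP 5.3 applies no multiplicity adjustment to them.

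**What to change.** In SAP 4.4, 11.3.3 and 11.3.4.1, use one window for the numerator and denominator of each rate. Either choice removes the problem:

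- **Keep Week 52.** Define exposure as (min(last dose date, Week 52 date) − first dose date + 1)/365.25 for PEY, or the same number of days divided by 28 for patient-months. Count missed sessions and RBC packs only to that same date.
- **Drop Week 52.** Remove the limit from the two headings in 4.4, and use whole-treatment counts with whole-treatment exposure. This agrees with Protocol 7.3 and with the count in 11.3.4.1.

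With either choice, give a formula for patient-month exposure, and state in 11.3.3 whether the comparison is on days or on days per PEY.

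The cost is a few sentences in the SAP and, under the first choice, one capped exposure variable. No new data are needed. It should be settled before the rates are produced, so that the window is not chosen with open-label results in view.

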4.5 SAFETY ASSESSMENTS

Study-specific safety will be assessed by evaluating the following:

- Occurrence of treatment emergent adverse events (TEAEs), treatment emergent serious adverse events (TESAEs) and clinically significant laboratory values
- Changes from Baseline in vital signs, electrocardiogram (ECG) findings, and clinical laboratory values.
- Safety interpretation will also be made based on analyses of composite endpoints derived from pre-specified and adjudicated events pooled across multiple studies in the roxadustat Phase 3 program. The members of an independent adjudication committee blinded to treatment assignment will adjudicate the following events in multiple phase 3 studies. Death from any cause, MI, stroke, heart failure requiring hospitalization, unstable angina requiring hospitalization, hypertensive emergency, deep venous thrombosis, pulmonary embolism, and vascular access thrombosis.

- Safety analyses based on these adjudicated events will be pooled across multiple studies. The analyses of the adjudicated events will be detailed in the pooled SAPs.

5 GENERAL STATISTICAL CONSIDERATIONS

5.1 SAMPLE SIZE DETERMINATION

The sample size calculation is based on the primary endpoints for the US (FDA) submission and Ex-US submission.

During the course of this study, which is being conducted in parallel with other Phase 3 studies, approximately 1000 subjects were to be enrolled to contribute to safety evaluation of roxadustat in comparison to epoetin alfa in CKD patients on dialysis less than 6 months. The final number of patients to be enrolled in this study will be based on the enrollment rate of other roxadustat phase 3 studies on dialysis patients, in order to optimize program timeline to generate sufficient adjudicated safety data across dialysis studies.

With at least 600 subjects, the study will provide at least 99% power to demonstrate statistical non-inferiority of roxadustat versus ESA in the primary endpoint for US (FDA) submission (i.e., specifically, Hb change from baseline to the average level during the evaluation period defined as Week 28 until Week 52). This assumes a difference (roxadustat minus ESA) of -0.30 g/dL, a non-inferiority margin for this difference of -0.75 g/dL (see Appendix 6 for the NI margin justification) and a standard deviation of 1.25 g/dL. This endpoint will be analyzed using the ITT population for the US (FDA) submission.

The study will provide at least 99% power to demonstrate statistical non-inferiority of roxadustat versus ESA in the primary endpoint outside of the United States (i.e., specifically, the proportion of subjects who achieve a Hb response at two consecutive visits during the first 24 weeks of treatment, without rescue therapy within 6 weeks prior to the Hb response). This assumes an 80% responder rate for both roxadustat and epoetin alfa, in order to support the primary efficacy analysis (i.e., a non-inferiority comparison in responder rate between roxadustat and epoetin alfa) and assuming a non-inferiority margin of -15% for this difference (roxadustat minus epoetin alfa).

Appendix 6 has description on the justification that the non-inferiority margin that were used.

5.2 ANALYSIS POPULATIONS

5.2.1 Intent-to-treat (ITT) Population

The ITT population will consist of all randomized subjects. If treatment received differs from the randomized treatment, the randomized treatment assignment will be used.

5.2.2 Safety Population

The Safety Population will consist of all randomized/enrolled subjects who received at least one dose of study medication. If treatment received differs from the randomized treatment, the actual treatment will be used for the safety analysis.

